3.3 Determine risk factors for serious illness with COVID-19 among patients receiving dialysis

By following outcomes of participants who are diagnosed with COVID-19 during the study, we will be able to determine risk factors for serious illness requiring hospitalization. This will further enable identification of the subgroup requiring aggressive and early therapy with antivirals or monoclonal antibodies.

[figure not shown]

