2.1 Patients receiving dialysis are an underserved, medically vulnerable population

The average patient on dialysis in the US is between 65-74 years old and has advanced diabetes causing kidney failure(1). Among patients on hemodialysis, 47% have diabetes as the primary cause ESKD, 62% have cardiovascular disease, and 32% have heart failure. Patients receiving dialysis are also disproportionately from racial/ethnic minority groups(1, 2). One striking piece of data encapsulates the disproportionate burden of ESKD on minority populations: 12% of persons in the US self-identify as Black; in contrast, 30% of patients on dialysis are Black.

Thirty-five percent of patients on dialysis in the US live in poor neighborhoods (i.e., neighborhoods with 20% of persons living below the federal poverty line)(3). In a seminal analysis, Volkova et al.(4) determined that persons living in poor neighborhoods had 3 to 5-fold higher likelihood of incident ESKD (compared with neighborhoods with < 5% of persons living below the poverty line), with larger risks experienced by Blacks compared with whites.

Requirement for in-center visits to complete dialysis can amplify the risk for SARS-CoV-2 transmission within the facility and in the community(5). Patients wear masks but may need to take them off to ingest prescribed medications and nutritional supplements; they have interactions in lobbies with friends on dialysis, often their only social interaction of the day. As with the rest of the US population, 40% of patients receiving dialysis with SARS-CoV-2 infection may be asymptomatic(6), potentiating the risk for transmission. Corbett et al.(5) report from the UK that dialysis facility characteristics such as distance between dialysis chairs, waiting room size, and staff symptomatic illness all correlated with facility COVID-19 cases. In the context of the COVID-19 pandemic this setup is a worst case scenario: a highly comorbid, elderly and socially disadvantaged population, with impaired immune responses and frailty, sharing small indoor spaces for prolonged periods.(7, 8)

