5.0 STUDY DESIGN

5.1 Study Overview

We plan a pragmatic cluster randomized clinical trial at the dialysis facility-level. We will compare rtPCR SARS-CoV-2 screening performed at a static (every two weeks) frequency versus a dynamic frequency (ranging from once a week to once every four weeks) anchored to county COVID-19 case rates among patient dialyzing at up to 62 facilities within US Renal Care (**Figure 1**). This design builds on a recently supported NIDDK initiative – the pragmatic facility-based cluster randomized trial. The Time to reduce Mortality in End-stage Kidney Disease (TiME) trial (<https://jasn.asnjournals.org/content/30/5/890/tab-article-info>) showcased the ability of dialysis facilities to provide accurate and complete clinical data for exposures and outcomes (death and hospitalizations), the willingness of >99% of patients to participate in and share clinical data using an 'opt out' consent, and feasibility of implementation without on-site research staff.

[figure not shown]

Figure 1. Study overview

Anterior nares rtPCR SARS-CoV-2 tests will be offered to all patients in the selected facilities (at a frequency decided by the randomization procedure). Patients may decline tests at any time during the 3-month study period. We will record test acceptance (primary outcome of the study). If a participant accepts the test, results will be relayed back to the patient and the facility within 48 hours. Patients with positive tests will be cared for as per standard facility procedures: asymptomatic persons will be advised to quarantine and will be isolated during dialysis to prevent further transmission, and symptomatic persons will be considered for antiviral therapy or referral to higher level of care based on the most updated Centers for Disease Control and Prevention guidelines.

After study completion, in addition to clinical data from the electronic health record, responses to the In-Center Hemodialysis Consumer Assessment of Healthcare (ICH CAHPS) of patients dialyzing at participating facilities will be tracked. Since participants are familiar with this survey and it is mandated to be implemented biannually, its use fits within the pragmatic framework of the trial.

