5.4 Inclusion/Exclusion Criteria

Inclusion Criteria

For Facility

- An established US Renal Care in-center hemodialysis facility located in a county with at least two US Renal Care facilities
- Facility governing board willingness to participate

Patient

- Treatment at US Renal Care in-center hemodialysis facility
- Age ≥ 18 years

Exclusion Criteria

Patient

- Unwillingness to share limited PHI clinical data using the electronic health record (EHR). If a patient declines offered testing he/she will still be part of the analyses as long as he/she is willing to share clinical data.
- Dementia or cognitive impairment, with inability to comprehend 'opting out' of participation

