5.6 Static Testing Frequency

In discussion with the US Renal Care medical officers regarding feasibility of integrating universal testing into routine clinical care, and given that test acceptability is our chief outcome of interest, we will offer patients dialyzing in the facilities randomized to the static arm rtPCR testing once every two weeks.

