5.7 Dynamic Testing Frequency

Facilities randomized to the dynamic arm will offer dialyzing patients rtPCR testing according to an adaptive testing strategy based on current estimates of community COVID-19 transmission. We anticipate that community transmission and risk of COVID-19 will evolve over the lifetime of this trial. Wastewater SARS-CoV-2 RNA loads can be used to detect COVID-19 incidence rates as low as 1 per 100 000 persons and have been demonstrated to correlate with clinical case data during the COVID-19 pandemic (Wolfe 2021, Karthikeyan 2021, Graham 2021, Huisman 2022). We will combine disease surveillance estimates based on wastewater samples with community surveillance data from the CDC to monitor current epidemic trends at the county level and guide testing strategy assignment in real time.

Using data from the preceding week, we will establish testing frequency for each facility for a period of four weeks. Facilities with high, medium, and low evidence of community COVID-19 transmission will be assigned to once weekly, once every two weeks, and once every four weeks testing respectively. After each four-week intervention period, facilities will be assigned a new testing strategy based on the current county level of COVID-19 transmission.

The data that will inform the facility assignment to testing strategies will be:

- 1) SARS-CoV-2 RNA wastewater percentile levels
Or
- 2) Number of new cases per 100,000 persons
Or
- 3) Number of hospitalizations per 100,000 persons

High, medium and low evidence of community COVID-19 transmission will be determined by pre-defined thresholds in these indicators (Table 1). If indicators suggest different transmission levels, the highest level is selected, with facilities falling into the highest frequency of testing when any one of the indicator criteria are met.

If at any given time during the trial, 95% of facilities do not meet criteria for high frequency testing then facilities will be assigned to testing frequency strategies using trial-wide tertiles of current COVID-19 incidence.

Table 1. Thresholds for levels of community COVID-19 risk by indicator

Community Risk Level	Wastewater	Clinical indicators	
	Viral percentile level ^a	New COVID-19 cases ^b	New COVID-19 hospitalizations ^b
Low	< 20 %	<50	<10
Moderate	20–59 %	50–199	NA
High	≥ 60 %	≥200	≥10

^a SARS-CoV-2 RNA wastewater levels with respect to local historical range

^b Total number per 100 000 persons in the past 7 days

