7.5 Testing at Ascend Clinical Laboratory

Patients receiving in-center dialysis have monthly laboratory testing performed, while undergoing dialysis and without requiring needlestick/phlebotomy. The monthly laboratory tests are standard of care and inform dialysis prescription and medication changes (e.g., hemoglobin informing use of erythropoietin stimulating agents). Ascend Clinical Laboratory (<http://clinical.aclab.com/about-us/>) is a fully accredited, CLIA certified laboratory with a throughput of more than 2 million tests per month. Ascend Clinical serves as the contract central laboratory for US Renal Care for these tests, as well as for the symptomatic in-facility anterior nares rtPCR testing that is already in place at US Renal Care. The two partners have established processes for sample collection, shipment and electronic health record communication for release

of health results. Ascend Clinical will ship sample collection kits to selected facilities. US Renal Care staff will follow standard procedures for collection, labeling and shipment back to Ascend Clinical Laboratory. Results will be released into the electronic health record system with an expected time frame of < 48 hours (i.e., prior to the return of the patient to the facility for dialysis).

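### Objective 3.3 looks for risk factors only among diagnosed patients, so a factor linked to refusing screening can look like a risk factor for serious illness when it has no effect on severity

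*Combined protocol and SAP*

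**What the plan says.** Section 3.3 states the objective and its population together: "By following outcomes of participants who are diagnosed with COVID-19 during the study, we will be able to determine risk factors" for illness requiring hospitalization. It adds that the result will help identify a subgroup for early, intensive treatment.

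The documents describe more than one way to be diagnosed:

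- **Study screening, which is voluntary.** Section 5.1: "Patients may decline tests at any time during the 3-month study period".
- **The screening interval, which varies.** In the static arm, "we will offer patients dialyzing in the facilities randomized to the static arm rtPCR testing once every two weeks" (section 5.6). In the dynamic arm, facilities with high, medium and low community transmission "will be assigned to once weekly, once every two weeks, and once every four weeks testing respectively" (section 5.7).
- **Testing outside the study.** Section 7.5 refers to "symptomatic in-facility anterior nares rtPCR testing that is already in place at US Renal Care".

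Section 2.1 says that "40% of patients receiving dialysis with SARS-CoV-2 infection may be asymptomatic". Section 5.4 keeps refusers in: "If a patient declines offered testing he/she will still be part of the analyses as long as he/she is willing to share clinical data". Under section 3.3, however, a refuser counts only once diagnosed.

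Hospitalizations, with admission and discharge diagnoses, come from the electronic health record (section 5.10). Section 7.7 lists screening offer and result dates, test results, COVID-19 dates and patient covariates. Section 7.10 covers the acceptability comparison and the effect of the intervention on death or hospitalization. It contains no analysis for objective 3.3.

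**The concern.** Patients who accept screening add asymptomatic and mild infections to the diagnosed group. Patients who decline add mainly infections that came to notice through symptoms or admission. If hospitalized cases are found either way, the hospitalized share of diagnosed patients is higher among decliners even when severity per infection is the same. A characteristic that goes with declining then picks up an association with serious illness that comes from detection.

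What is at stake is the use that section 3.3 makes of the result. A subgroup put forward as needing early treatment could partly consist of patients who are less often swabbed. The primary acceptability comparison and the arm comparisons of death and hospitalization do not use this population and are not affected.

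**Working it through.** The plan gives no figure for objective 3.3, so there is none to reproduce. The check asks what risk ratio a factor with no true effect on severity would show among diagnosed patients.

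**Inputs**

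- A = 0.40, asymptomatic share of infections (section 2.1).
- Acceptance a = 0.40 vs 0.65. These are arm-level planning values from section 5.5, borrowed here as an assumed contrast between two levels of a patient factor. The documents give no acceptance by patient characteristic.
- Acceptance 0.30 vs 0.80: an assumed wider contrast.
- d = chance that screening detects an infection. It depends on acceptance, interval and how long an infection stays detectable (not given; 10 days assumed in step 2).
- s = chance that a symptomatic but non-hospitalized case is diagnosed without screening (not given; range 0.4 to 1).
- h = true hospitalization risk per infection (assumed 0.15 to 0.30).
- Hospitalized cases are always diagnosed (relaxed in step 5).

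**Formula**

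P(hospitalized | diagnosed) = h / [h + (1 − A − h)(1 − (1 − s)(1 − d)) + A·d]

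With s = 1 the denominator is 0.6 + 0.4d. The false risk ratio is then the ratio of diagnosed shares, whatever h is.

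**1. All symptomatic cases diagnosed, d = a** (for example, infections detectable for 14 days under two-weekly offers)

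- 40% vs 65%: (0.6 + 0.26)/(0.6 + 0.16) = 0.86/0.76 = 1.13.
- 30% vs 80%: 0.92/0.72 = 1.28.

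**2. Same, with a 10-day window and two-weekly offers**, so d = (10/14)a

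- 40% vs 65%: d = 0.286 and 0.464; 0.786/0.714 = 1.10.
- 30% vs 80%: d = 0.214 and 0.571; 0.829/0.686 = 1.21.

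**3. Some symptomatic cases missed** (s = 0.4, d = 0.40 vs 0.65)

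- h = 0.15: denominators 0.15 + 0.45 × 0.64 + 0.16 = 0.598 and 0.15 + 0.45 × 0.79 + 0.26 = 0.7655; ratio 1.28.
- h = 0.30: 0.797/0.652 = 1.22.

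**4. A factor that truly lowers severity** (d = 0.40 with the factor, 0.65 without; h = 0.20 without)

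- True ratio 0.8, s = 1: (0.16/0.76)/(0.20/0.86) = 0.91; with s = 0.7, 0.96.
- True ratio 0.5: 0.57 (s = 1) and 0.61 (s = 0.7).

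**5. Severe cases not always diagnosed.** Let q be the chance that a hospitalized case is diagnosed without screening; h = 0.20, s = 1, d = 0.40 vs 0.65.

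- q = 0.4: (0.128/0.688)/(0.158/0.818) = 0.96.
- q = 0: (0.08/0.64)/(0.13/0.79) = 0.76.

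**6. Testing interval.** With a 10-day window, a = 0.40, s = 0.7 and h = 0.20, d is 0.503, 0.286 and 0.143 for weekly, two-weekly and four-weekly offers. The observed risk among diagnosed patients is 0.27, 0.32 and 0.36, against a true 0.20.

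**The case against.** **Section 3.3 is a short statement of aim, with no model, and is absent from the outcome lists in the overview and section 5.10.** On this view the gap is missing detail, and the data in section 7.7 leave adjustment open. It is true that adjustment is possible. But the population is stated, the objective is not labelled exploratory, and section 7.10 plans no adjustment. Following the text as written gives the bias.

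**A reader might infer that every factor linked to refusal will look harmful.** The figures do not support that. The effect is a shift: truly protective factors still look protective in step 4. An upward direction also requires severe cases to be diagnosed largely regardless of screening. Routine symptomatic testing (section 7.5) and record-based hospitalization data (section 5.10) make this plausible, but no rate is given, and step 5 shows the shift shrinking or reversing.

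**A reader might infer that trial arm itself biases the risk factors.** Arm is randomized by facility. A different detection rate between arms changes the overall apparent severity but does not by itself bias a factor balanced across arms. Interval matters most for factors tied to county transmission within the dynamic arm.

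**The size rests on assumed contrasts.** This stands. No acceptance difference by patient characteristic is documented, refusal is made offer by offer, and section 5.9 describes surveillance testing as already standard, which would narrow the gap. In the other direction, the ICC of 0.5 in section 5.5 implies a between-facility SD of √(0.5 × 0.4 × 0.6) = 0.35. A 30% vs 80% contrast is thus about 1.4 facility SDs, although that is spread between facilities, not between levels of a patient factor.

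**Part of an association with refusal may be real,** since refusing a test may delay treatment. This also stands, and no model here fully separates the two.

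**Conclusion.** The concern holds as a foreseeable detection bias in objective 3.3 that the plan does not handle. A factor linked to refusing tests can look like a risk factor with no effect on severity.

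At the borrowed 40% vs 65% contrast, the false ratio is about 1.10 to 1.13 if all symptomatic cases are diagnosed, and up to about 1.28 if only 40% of the non-hospitalized ones are. At 30% vs 80%, with all symptomatic cases diagnosed, it is about 1.2 to 1.3. Only the 40% asymptomatic share is a documented input about infection. The contrasts across factor levels, the detection window, s and h are assumptions. So is the near-complete diagnosis of severe cases, on which the upward direction depends.

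The shift is modest at the planning values. It should still be corrected, because section 3.3 means to define a treatment subgroup from the result and the correction is cheap.

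**What to change.** In sections 3.3 and 7.10:

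1. Keep the severity model in diagnosed patients, and adjust it for screening exposure before diagnosis: number of offers, number accepted, testing interval and arm. Count only up to diagnosis, because total tests taken can be cut short by admission or death. State how patients with no offer before diagnosis are handled.
2. Beside it, report a model of COVID-19 hospitalization in all enrolled patients, including those who decline testing, from the electronic health record.
3. Show results by route of detection (study screening or clinical diagnosis) descriptively only. Route partly reflects symptoms, so conditioning on it can add bias.
4. State that factors not consistent across the two models will not be used to define the subgroup named in section 3.3.

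The cost is SAP wording and one extra model, with no new data. The all-enrolled model mixes risk of infection with risk of severity, so it supports the diagnosed-only model and does not replace it. Adjustment for screening exposure may also remove any real effect of refusal through later treatment, and the report should say so.

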4.0 STUDY ORGANIZATION

4.1 Collaborating Institutions

Key investigators are outlined in below figure. Three organizations will work integrally: study design input will come from Stanford, followed by patient-facing implementation at US Renal Care facilities with laboratory support from Ascend Clinical Laboratory. Stanford University investigators are physicians, epidemiologists, health policy experts, statisticians, and clinical trialists who are well qualified to design and implement the proposed study, with established

[figure not shown]
processes for ethical conduct of research, handling protected health information (PHI), and study analysis. US Renal Care is a for profit dialysis network with over 350+ nationwide dialysis facilities, and actively participates in multiple clinical trials and epidemiology studies to advance the health care of patients receiving dialysis. Finally Ascend Clinical is a CLIA-certified, high throughput clinical laboratory specializing in testing for patients receiving dialysis; this laboratory processes more than 2 million tests per month.

US Renal Care and Ascend Clinical will transfer data with limited protected health information (PHI) to Stanford University. Stanford University investigators will be responsible for data preparation, analysis, and transfer to NIH RADx-UP. The “Rapid Acceleration for Diagnostics Program (RADx) Institutional Certification” for studies using data generated for the RADx program, is located in the Appendix. In addition, Abbott Molecular will discount the anterior nares rtPCR testing kits and associated supplies (Alinity m SARS-CoV-2 assay).

4.2 Role of RADx-UP

The NIH RADx-UP consortium (<https://radx-up.org/about/>) is funded by the NIH National Institute on Minority Health and Health Disparities. The goal of the consortium is to engage community and academic partnerships to expand availability of SARS-CoV-2 testing in underserved communities. As of January 2022, there are over 100 projects occurring throughout the country. As part of the consortia, participating institutions are required to collect and share data on a set of “Common Data Elements”: <https://radx-up.org/learning-resources/cdes/>. Furthermore, studies receive support in terms of translation, materials to enhance test uptake, and logistical support for procuring tests.

5.0 STUDY DESIGN

5.1 Study Overview

We plan a pragmatic cluster randomized clinical trial at the dialysis facility-level. We will compare rtPCR SARS-CoV-2 screening performed at a static (every two weeks) frequency versus a dynamic frequency (ranging from once a week to once every four weeks) anchored to county COVID-19 case rates among patient dialyzing at up to 62 facilities within US Renal Care (**Figure 1**). This design builds on a recently supported NIDDK initiative – the pragmatic facility-based cluster randomized trial. The Time to reduce Mortality in End-stage Kidney Disease (TiME) trial (<https://jasn.asnjournals.org/content/30/5/890/tab-article-info>) showcased the ability of dialysis facilities to provide accurate and complete clinical data for exposures and outcomes (death and hospitalizations), the willingness of >99% of patients to participate in and share clinical data using an 'opt out' consent, and feasibility of implementation without on-site research staff.

[figure not shown]

Figure 1. Study overview

Anterior nares rtPCR SARS-CoV-2 tests will be offered to all patients in the selected facilities (at a frequency decided by the randomization procedure). Patients may decline tests at any time during the 3-month study period. We will record test acceptance (primary outcome of the study). If a participant accepts the test, results will be relayed back to the patient and the facility within 48 hours. Patients with positive tests will be cared for as per standard facility procedures: asymptomatic persons will be advised to quarantine and will be isolated during dialysis to prevent further transmission, and symptomatic persons will be considered for antiviral therapy or referral to higher level of care based on the most updated Centers for Disease Control and Prevention guidelines.

After study completion, in addition to clinical data from the electronic health record, responses to the In-Center Hemodialysis Consumer Assessment of Healthcare (ICH CAHPS) of patients dialyzing at participating facilities will be tracked. Since participants are familiar with this survey and it is mandated to be implemented biannually, its use fits within the pragmatic framework of the trial.

5.2 Sampling Procedures

We will narrow the sampling frame to counties with at least two US Renal Care facilities. We will then select the paired facilities for randomization, oversampling by 30%. Sampling from

counties with at least two US Renal Care facilities ensures balance in socio-demographics of randomized facilities without sacrificing geographic diversity.

